1.0 Study Summary

Study Title	Enhancing Sexual Safety: Couples' Communication and HIV Testing Among YMSM (WE TEST)
Study Design	Comparative Effectiveness Trial (CET), Randomized Control trial (RCT)
Primary Objective	We will conduct a comparative effectiveness trial (CET) of CHTC for adolescent-age (15-24 years) same-sex male couples. This design tests the added benefits of adjunct intervention components delivered prior to receipt of CHTC-Assertive Communication Training (ACT) videos viewed by the couple together and individually delivered Motivational Interviewing-based Communication Skills Training (MI-CST). These target the development of communication skills necessary to participate fully in HIV prevention and sexual safety discussions inherent to CHTC. This project will assess a continuum of intervention packages to address the developmental needs of YMSM (CHTC; ACT videos + CHTC; MI-CST + ACT videos + CHTC) to identify which package optimizes outcomes while minimizing delivery cost.
Secondary Objective(s)	Test a sustainable model of CHTC implementation in real world adolescent HIV clinics. In line with the implementation science focus of SIU U19, we utilize the EPIS to guide our implementation strategy. We will work with SIU Analytic Core's (AC) health-economist, [name], to conduct cost-effectiveness analyses to inform implementation decision-making. In collaboration with SIU ISC, we will document provider feedback to training and intervention materials to modify materials and create training packages for broad dissemination.
Research Intervention(s)	We are comparing three conditions for HIV testing with adolescents and young adults: Couples HIV Testing and Counseling (CHTC), CHTC-Assertive Communication Training (ACT), and Motivational Interviewing-based Communication Skills Training (MI-CST). These will test the ways in which including communication training improves upon existing HIV testing services.
Study Population	Adolescent-age (15-24 years) same-sex male couples
Sample Size	Phase 2 (n=36 couples → 72 individuals) Phase 3 (n=200 individuals)
Study Duration for individual participants	Phase 2: 3 months; Phase 3: 6 months
Study Specific Abbreviations/ Definitions	Adolescent Medicine Trials Network (ATN) Comparative Effectiveness Trial (CET) Couples HIV Testing and Counseling (CHTC) Individual HIV testing and Counseling (IHTC) CHTC-Assertive Communication Training (ACT) Motivational Interviewing-based Communication Skills Training (MI-CST) Young men who have sex with men (YMSM)

PROTOCOL TITLE:

2.0 Objectives*

Aims: We will conduct a comparative effectiveness trial (CET) of Couples HIV Testing and Counseling (CHTC) for adolescent-age (15-24 years) same-sex male couples. This design tests the added benefits of adjunct intervention components delivered prior to receipt of CHTC-Assertive Communication Training (ACT) videos viewed by the couple separately and individually delivered Motivational Interviewing-based Communication Skills Training (MI-CST). These target the development of communication skills necessary to participate fully in HIV prevention and sexual safety discussions inherent to CHTC. This project will assess a continuum of intervention packages to address the developmental needs of YMSM (CHTC; ACT videos + CHTC; MI-CST + ACT videos + CHTC) to identify which package optimizes outcomes while minimizing delivery cost.

Aim 1: Conduct a sequence of randomized control trials (RCTs) to evaluate the acceptability, feasibility, and comparative effectiveness of novel treatment packages.

Aim 1a: In study Phase 2, we will conduct a pilot RCT to evaluate the acceptability and feasibility of adjunct intervention components. This initial trial will recruit n=36 couples who will be randomized to one of 3 conditions: Condition 1: CHTC (only); Condition 2: couples' joint observation of ACT videos + CHTC; Condition 3: each individual within couple receiving MI-CST + joint observation of ACT videos + CHTC. Youth will then complete follow-up assessments at 1 and 3 months post-intervention. YOUTH DO HAVE THE OPTION OF COMPLETING THE INTERVENTION ON THEIR OWN IF THEY CAN NOT GET THEIR PARTNER TO AGREE TO PARTICIPATE. During Phase 3, we will recruit 200 individuals into a CET with two conditions: Condition 1: the optimum adjunct intervention package identified in Phase 2 and Condition 2: Individual HIV Testing (IHTC) as usual. Youth in this CET will complete follow-up assessments at 1, 3, and 6 months. Youth have the choice of attending the baseline visit alone or with their partner and have the option to bring their partner in later after completing the baseline alone.

Aim 1b: Assess self-management model; we posit that assertive communication skills will mediate intervention effects at all follow-ups. In study Phases 2 and 3, we anticipate between-condition differences will be greatest among YMSM with poor baseline assertive communication.

Aim 2: Test a sustainable model of CHTC implementation in real world adolescent HIV clinics. In line with the implementation science focus of SIU U19, we utilize the EPIS to guide our implementation strategy. We will work with SIU Analytic Core's (AC) health-economist, [name], to conduct cost-effectiveness analyses to inform implementation decision-making. In collaboration with SIU ISC, we will document provider feedback to training and intervention materials to modify materials and create training packages for broad dissemination.

We will achieve our aims over two phases of the study.

PROTOCOL TITLE:

Phase 2 (n=36 couples): involves a pilot randomized control trial (RCT) to evaluate the acceptability, feasibility, and preliminary efficacy of these adjunct components.

Phase 3 (n=200 individuals): involves a CET comparing the most promising intervention package from Phase 2, consisting of individual MI, ACT video+ a recognition survey, and CHTC, compared to individual HIV testing and counseling (IHTC) delivered as usual. Participants in either condition can come as an individual or with their partner or come first as an individual and then bring their partner. This phase is focused on Implementation and Sustainment phases of the EPIS model informed by outcome analyses, cost analyses, and feedback from youth and ATN staff.

Phase 3 has now been added to this protocol document.

Hypothesis: The primary hypothesis is that because of developing skills in self-management and assertive communication, inclusion of adjunct components will be associated with clinically significant decreases in HIV transmission risk behavior as compared with partnered YMSM who receive individual testing and counseling (only). Secondarily, we propose that these intervention effects will be mediated by assertive communication skills.

3.0 Background*

Partnered young men who have sex with men (YMSM) are a uniquely vulnerable population. Adolescents in relationships continue to be an under-examined subgroup, despite the fact that YMSM (age 15-24) are at among the highest risk of HIV infection. Among men who have sex with men (MSM) age 18 and older, 35–68% of new HIV infections are transmitted between partners in primary (vs. casual) relationships. Of concern, primary partners account for 79% of new infections within the youngest MSM cohort.

Primary partner HIV transmission can result from a higher number of sex acts, more receptive anal intercourse, and lower condom use with primary (vs. casual) partners. Despite this elevated health risk, partnered MSM paradoxically perceive themselves to be at much lower risk of HIV infection, and test for HIV less often. Concomitantly, condom use may be suppressed with primary partners because condomless anal sex (CAS) is often interpreted as an indicator of commitment and emotional closeness. In fact, data reflect a strong, positive association between CAS and relationship seriousness for YMSM. Critical within this cohort, relationship development is still new, and romantic partnerships tend to be of short duration. Thus, frequent brief primary partnerships, low perception of CAS risk, and new negotiation of communicating emotional closeness during this developmental period may all escalate HIV infection among partnered YMSM.

Multilevel Intervention Integrating Couples Interdependence Theory (CIT) and Self-Management Theory as a framework for effective service delivery to partnered YMSM. We conceptualize individual HIV prevention (including HIV testing) in the self-

PROTOCOL TITLE:

management framework. Here, problem solving, decision making, and access to care collectively predict health behavior engagement. This in turn develops positive provider relationships that facilitate behavioral skills development and access to care. While useful, the self-management framework does not fully address or incorporate the inherently multilevel and dyadic nature of sexual health decision-making for partnered YMSM. Fortunately, this omission is addressed in Couples Interdependence Theory (CIT). Within CIT, health positive outcomes are proposed to require the coordinated effort of both partners, and partners must accommodate potentially divergent health and safety preferences. Dyads with partners who balance self-interests with relationship-interests are more successful at conflict resolution, including HIV risk management. Work by Protocol Lead (PL) [name] and others, reflects that one strategy by which gay couples accommodate sexual health goals is through negotiating sexual agreements (e.g., rules and boundaries for outside partners).

The process of accommodation generally, and negotiation of sexual agreements specifically, requires advanced and flexible conceptual and communication skills. To be effective, individuals must identify both their own and their partner's preferences and feelings, and then communicate those concepts in constructive ways. Couples HIV Testing and Counseling (CHTC) successfully enhances sexual agreement communication with adult MSM by utilizing CIT. However, CHTC has not been examined with young samples. Yet, this intervention may play a critical role because of their level of cognitive and social development (e.g., still emergent communication skills). Youth may need added support to effectively identify sexual goals and to learn to communicate them carefully and productively, and this support may come in the form of CHTC and additional communication skills training.

Excitingly, our team has expertise across both the use of CHTC among partnered MSM (R34 DA036419 PL [name]) and support of partnered adolescents in communicating sexual and HIV risk reduction goals to their sexual and relationship partners. This is relevant, because data reflect that less than half of partnered adolescents feel comfortable advocating for and discussing condom use before sexual intercourse, contributing to 50% of youth consenting to CAS, despite wanting to use a condom. YMSM show even lower rates of assertive communication relative to heterosexual age-mates. Enhancing communication skills is thus a route to improve sexual safety in this age group.

4.0 Study Endpoints*

The primary goals of this study is to help participants reduce their HIV transmission risk behaviors by increasing their communication skills with their partners, which could lead to fewer number of sex acts, less receptive anal intercourse, and higher condom use with primary (vs. casual) partners.

5.0 Study Intervention

Intervention Design and Procedures: The primary innovation of this multilevel CET lies in the novel packaging of existing interventions in a manner that addresses the

PROTOCOL TITLE:

specific developmental needs of YMSM. While MI-CST, video based ACT, and CHTC have individually established efficacy, this study will be the first to evaluate a continuum of prevention packages, which combine these components. In addition, this multilevel intervention seeks to leverage the power of the dyadic processes to enhance motivation for HIV testing and prevention (including biomedical prevention). Our adjunctive components (ACT and MI-CST) are specifically intended to enhance self-management skills (e.g., assertive communication) which are essential to effectively engage relationship partners in collaborative sexual goal development and problem solving. The underlying assumption of this strategy is that improvements in dyadic functioning will lead to reductions in sexual risk for both individuals within the relationship. Finally, we make innovative use of biomarkers to operationalize HIV-transmission risk. Our ability to draw conclusion about intervention effects is enhanced by examining biomedical and behavioral outcomes for both sexual partners regardless of relationship dissolution; this is critical to enhance sexual safety for both individuals of a couple, particularly in light of the short duration and rapid re-partnering of YMSM during this developmental period.

Intervention Training and Supervision: Following Phase 1, to prepare for the roll out of the CET, we will hold a week-long in-depth training on all study procedures. This training will include members of the two ATN sites where CHTC will be implemented in Phase 2. Any staff who cannot attend due to non-resolvable travel restrictions will participate via Skype. This training will include a 2-day training in CHTC (overseen by PL [name]), 2-day training on MI (overseen by PL [name]), and 1 day dedicated to reviewing/practicing protocol delivery, including administration of the ACT videos. Throughout training and fidelity monitoring activities, the implementation team, including the study PLs, will work closely with the SIU ISC to document CHW and supervisor performance and feedback on intervention materials and delivery (reflecting the Exploration and Preparation phases of EPIS). At the conclusion of the CET, the project implementation team will work closely with the ISC to package training and intervention materials in a manner that supports the dissemination of CHTC and adjunct components shown to be effective.

We will build upon the existing ATN infrastructure to complete this in a parallel model to SIU U19. Here, we will use a train-the-trainer model, where CHW supervisors will be brought to OHSU to be trained in implementation and delivery, with the goal that they will serve as local implementation “champions” by instructing and overseeing implementation within their ATN clinics. To maximize accuracy, consistency, and fidelity of intervention delivery, each intervention (CHTC; ACT; MI-CST) will be codified into manuals.

This training sequence will be offered again prior to Phase 3 in order to bring new ATN sites online and update staff at existing sites.

Ongoing supervisor's conference call. PL [name] has a demonstrated track-record of training and supervising clinical interventions in real-world practice sites, including MI, from a distance. Using the same model proposed here with rural school-based health providers (NHLBI R01; PL [name], Co-Lead [name]), PL [name]

PROTOCOL TITLE:

[name] has shown a high degree of clinical impact, fidelity, and integrity for execution of MI for the 5 year roll-out of the project. And active interventionist will work directly with the CHW supervisors during weekly clinical supervision calls. PLs [name] and [name] will be on the phone during these calls, but not actively participate. PLs [name] and [name] will then work directly with clinical supervisor to debrief any issues that arose during the calls. Clinical Supervisor will follow up with the CHW supervisors to address outstanding clinical issues. Similarly, as with [name] prior work in implementation science, in addition to weekly supervision meetings, clinical supervisor will visit each site annually, and greater frequency in situations where there is therapist drift, to practice the intervention approaches with study providers to get them back to parity with other CHWs. As with [name] successful work with rural adolescent medicine, this procedure has been supported with a high degree of clinical success and integrity in prior multi-site implementation science work with underserved adolescents.

Assurance of Intervention Fidelity: All sessions will be audio recorded for the purposes of systematic supervision so PLs can assess fidelity and prevent therapist drift. The PRIDE Research Consortium (formerly Center for HIV Educational Studies and Training (CHEST)) at Hunter College maintains a team of Motivational Interviewing Treatment Integrity (MITI) coders trained in the assessment of MI and [name] maintains a group of research assistants trained in the assessment of CHTC fidelity. These coders will review the first 10 sessions completed by each CHW and a random 20% of sessions for the remainder of the trial (approximately 25% of sessions completed by each CHW over the entire trial). Coding of all initial sessions will ensure fidelity across therapists at the start of the trial and subsequent coding will identify any therapist drift that occurs for the remainder of the trial. Tapes will be coded to ensure the presence of essential elements of the intervention. Consistent with procedures in our previous effectiveness trials, when therapists exhibit low levels of intervention integrity or significant drift, this feedback will be relayed to the on-site supervisor. The training team (PLs [name] and [name]) will then work with the local supervisor to develop a remediation plan to bring the CHW back up to parity with other interventionists. This process will be facilitated by regular contact with on-site supervisors as detailed in our training and implementation plan below.

6.0 Procedures Involved*

Enrollment and Consent: Utilizing enrollment procedures established within ATN, clinic staff will invite YMSM who present for HIV testing services the opportunity to screen. These interested index partners will complete a brief iPad eligibility screener.

For Phase 2, IF ELIGIBLE, THE SCREENER WILL RANDOMIZE THEM TO COMPLETE THE BASELINE AS A COUPLE OR AN INDIVIDUAL.

If randomized to individual, staff will schedule a baseline assessment for the invited youth. If randomized to couple, staff will schedule a baseline assessment for the invited youth at a time both they and their relationship/romantic partner are available. Partners

PROTOCOL TITLE:

will independently complete informed consent at the beginning of the baseline visit, prior to assessment following ATN-wide established protocols.

FOR PHASE 2, IF THE YOUTH IS RANDOMIZED TO COMPLETE THE BASELINE AS A COUPLE, AND THEY INDICATE THAT THEY WILL BE UNABLE TO HAVE THEIR PARTNER COME FOR THE APPOINTMENT, THEY WILL BE ALLOWED TO COME TO THE BASELINE AS AN INDIVIDUAL.

For Phase 3, study sites are given the options to deliver the intervention in-person as usual, or entirely remote delivery. This is to allow sites more flexibility surrounding COVID-19 closures and restrictions, which vary by site.

For Phase 3, index partners will be able to choose to attend their baseline appointment on their own or with their partner. While scheduling the baseline, staff will ascertain whether the participant is planning to come in alone or with their partner so they can reserve adequate time, space and resources for the appointment. Regardless of whether the index partner attends alone or with their partner, after the participant(s) complete the survey at the beginning of the baseline appointment, the index partner will be randomized to the We Test intervention or individual HIV testing (IHTC) as usual. If alone and randomized to the We Test intervention, the index partner will participate in the intervention as an individual. If both members of the couple attend and are randomized to We Test, they will participate in the intervention as a couple. If both members of the couple attend and are randomized to IHTC, they will each receive IHTC as usual. The index partner who participates as an individual (in either condition) will be offered the opportunity to bring their partner to participate in the WeTest. The partner will be enrolled into the same condition as the index partner.

Baseline Visit – PHASE 2 (up to \$50)

1. Informed Consent process
2. STI testing (\$20)
3. CASI survey (\$10)
4. Randomization to one of three conditions (phase 2)
5. Session 1 (phase 2): will occur at this time in accordance with the randomized condition.
 - a. Condition 1: CHTC
 - b. Condition 2: ACT videos + CHTC
 - c. Condition 3: MI-CST + ACT videos + CHTC

FOR COUPLES WHO ARE ASSIGNED TO A CONDITION THAT INCLUDES VIDEOS, PARTICIPATING COUPLES WILL WATCH THE VIDEOS SEPARATELY. AFTER VIEWING THE VIDEOS SEPARATELY, A VIDEO RECOGNITION SURVEY (ATTACHED) IS COMPLETED BY THE COUPLE TOGETHER.

Baseline Visit – PHASE 3 (up to \$50)

1. Informed Consent process
2. CASI survey (\$30)

PROTOCOL TITLE:

3. Randomization
4. HIV testing (\$10)
5. STI testing (\$10)
6. Session 1: will occur at this time in accordance with the randomized condition.
 - a. Condition 1: individual HIV testing (IHTC) as usual condition
 - b. Condition 2: We Test intervention

Randomization Stratification: Randomization will be stratified by Site, Age (either partner under 18 vs both 18 & older), Race/Ethnicity (Both White vs not both White) and whether the index partner attended individual vs couple.

After completing the baseline assessment for both Phases 2 and 3, YMSM will complete follow-up assessments a month after baseline, and 3 months after baseline. In Phase 3, participants will also complete assessments at 6-months post-baseline. Online CASIs will be completed at each follow-up either at home or in-office. In addition, STI and HIV testing will occur at the 3-month and 6-month follow-ups. All follow-ups will be conducted individually to facilitate retention, even if the couples dissolve.

Immediate Post-Test Assessment (1 month after BL)

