10.0 Subject Population*

Inclusion Criteria:

YMSM couples who express interest in We Test must demonstrate the following inclusion criteria to be enrolled in the study:

- At least one partner must be HIV-negative or status unknown
- THE INDEX PARTNER must be 15-24 years old
- YMSM under age 18 MUST HAVE AN AGE CONCORDANT PARTNER TO PARTICIPATE IN THIS STUDY, I.E., MINORS may only participate in the study with a partner within 2 years of age OF THE MINOR SUBJECT'S AGE. THE AGE CONCORDANT PARTNER MUST BE AT LEAST FIFTEEN YEARS OLD.
- INDEX PARTNER MUST BE SEXUALLY ACTIVE (ANY ACTIVITY THAT COULD LEAD TO ORGASM)
- CURRENTLY SEEING SOMEONE, DATING, EXPERIMENTING WITH RELATIONSHIPS OR IN A RELATIONSHIP
- HAVE HAD SEX, HOOKED UP WITH OR MADE OUT WITH THAT PERSON
- Both relationship partners must agree to attend an assessment together at an ATN affiliated clinic
- Both partners must be able to communicate in English.
- GENDER IDENTITY AS MALE OR nonbinary, GENDERQUEER, agender OR GENDER NONCONFORMING •MALE SEX AT BIRTH REMOVED ON 8.21.18
- "HAVE THAT PERSON'S AGE BE OVER 14 BUT WITHIN 2 YEARS OF INDEX PARTNER"; ALL PREVIOUS APPROVED CRITERIA STILL APPLY EXCEPT FOR THE AFORMENTIONED DELETED CRITERIA
- To participate in the intervention remotely, youth must be at least 17 and over the age of sexual consent in their state of residence. If participating as a couple, both must be over the age of sexual consent in their state. If a participant lives in the following states and want to participate remotely, they will need to be 18 years old: Arizona, California, Delaware, Florida, Idaho, North Dakota, Oregon, Tennessee, Utah, Virginia, and Wisconsin.

Exclusion Criteria:

YMSM couples will be excluded from the study if they indicate any of the following:

- Unstable, serious psychiatric symptoms
- Current suicidal/homicidal ideation
- Current or prior Intimate Partner Violence (IPV) on the part of either relationship partner
- IF EITHER PARTICIPATING PARTNER FELT PRESSURED OR COERCED TO PARTICIPATE IN THE STUDY OR FELT ANYONE MADE THEM FEEL THEY HAD TO PARTICIPATE IN THEY STUDY WHEN THEY DID NOT WANT TO.

We will include individuals who are not yet adults:

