13.0 Recruitment Methods

Recruitment and Screening: Leveraging existing ATN infrastructure, participants will be recruited and screened for eligibility via 2 different ATN sites in Phase 2 and 3 ATN sites in Phase 3 that provide HIV testing and prevention services to YMSM. All ATN clinics, as well as PRIDE, have extensive relations with the gay, lesbian, bisexual, and transgender communities, community service organizations, health service organizations, and providers for MSM. This may be supplemented by online advertising conducted through SIU's Recruitment and Enrollment Core (REC). Potential Participants may be identified at these local sites through testing services, outreach activities, and online social media and dating apps (e.g., Facebook, Instagram, Reddit, Tumbler, Grindr, Scruff, Adam4Adam, Jack'd). While advertising will be distributed through SIU's REC, they will be targeted to the geographic areas surrounding the ATN sites for this project and

PROTOCOL TITLE:

will contain information about participation at the ATN clinic. Given the shift to remote testing, intervention delivery, and study visits in Phase 3 due to COVID-19, recruitment via online advertisements will be expanded nationwide. Couples will be screened through an indexcase approach. One partner in the couple will be asked to provide screening information about themselves and their partner. If the couple is preliminarily eligible based upon the report of the index partner being screened, that index partner will be asked to schedule a baseline appointment. SCHEDULING WILL TAKE PLACE VIA EMAIL, TEXT MESSAGE, AND PHONE at a time both they and their partner can attend. Contact information for the index partner will be collected at this point and added in REDCap for tracking purposes.

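### Screening is described for the index partner only, and no stated step asks the partner about the couple-level exclusions before randomisation, a joint session or later enrolment

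*Protocol*

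**What the plan says.** Protocol section 6.0 (Enrollment and Consent) describes one screener and who completes it: "These interested index partners will complete a brief iPad eligibility screener". Section 13.0 describes an index-case approach: "One partner in the couple will be asked to provide screening information about themselves and their partner". What follows from that report is a baseline appointment, offered under this condition: "If the couple is preliminarily eligible based upon the report of the index partner being screened".

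Section 10.0 sets the exclusions for the couple: "YMSM couples will be excluded from the study if they indicate any of the following". The violence criterion is explicit about reach: "Current or prior Intimate Partner Violence (IPV) on the part of either relationship partner". The coercion criterion likewise covers either participating partner. Two others, "Unstable, serious psychiatric symptoms" and "Current suicidal/homicidal ideation", stand under the couple heading without repeating that they apply to either partner.

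The Phase 3 baseline list in section 6.0 runs from consent to the CASI survey, randomisation, HIV and STI testing and session 1, all at one visit. Couples who attend together and are allocated to We Test take the intervention together; couples allocated to IHTC are each tested individually. For an index who starts alone and brings a partner later, section 6.0 says: "The partner will be enrolled into the same condition as the index partner".

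**The concern.** The exclusions depend on facts that one partner may not know about the other, or may have reason not to report. An index cannot be relied on to know whether his partner has suicidal thoughts. An index who has been violent has a motive not to say so. Whether a partner felt pressured to take part is something only that partner can answer.

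Safety is the main stake. If the partner is never asked, a person who has been harmed could sit in a joint session on sexual agreements with the person who harmed him, which the violence exclusion is meant to prevent. Participants may be as young as 15, with parental permission waived.

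There is also a data consequence. Under section 14.0, a person found ineligible after baseline is taken off the follow-up call lists but stays in the retention denominators. Ineligibility that could have been found before allocation then becomes missing outcome data after it. Two of the four risk indicators in SAP section 1.2 are defined at couple level.

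**Working it through.** The point concerns procedure, so the check is to set the sections side by side and ask, for each place where the partner's eligibility could be confirmed, whether the text says that it is.

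1. **Screener (6.0, 13.0).** The index completes it and reports on both. The partner is covered by proxy.
2. **Preliminary status (13.0).** The word implies a later confirmation. The text then turns to scheduling; no confirming step is described.
3. **Consent (6.0, 21.0).** Each partner consents independently and in private. The stated purpose of the privacy is to limit pressure from a partner. The four comprehension questions in 21.0 cover study tasks, how to stop, what to do if distressed, and risks. None covers violence, ideation or psychiatric state.
4. **Survey before randomisation (6.0).** Attending participants complete it. The protocol does not say that it contains the exclusion questions, or that staff review the answers before allocation.
5. **Phase 3 baseline list (6.0).** There is no eligibility line between survey and randomisation, and session 1 follows at the same visit.
6. **Partner who joins later (6.0).** The only rule given concerns the condition: the partner takes the index's. No screening step is stated.
7. **Withdrawal table (14.0).** It has a category for ineligibility found during baseline, so eligibility can still fail there, but it names no step that would reveal this for the partner. Its category for ineligibility found after baseline gives as its example psychiatric conditions discovered while baseline data are being collected, and says such a person should have a condition assigned. The protocol thus itself foresees ineligibility that is evident in baseline data being acted on only after allocation.

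The only number the documents allow is a ceiling. Phase 3 plans 200 individuals. If all attended as couples, 200 / 2 = 100 would be non-index partners. The real number is lower to the extent that index partners attend alone, which section 6.0 permits. Of the couples who do attend, only those allocated to We Test have a joint session, and no allocation ratio is stated.

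**The case against.** The strongest case on the other side is that the protocol does not make the index's report final. Eligibility at that stage is preliminary; the partner then consents privately under network-wide procedures and completes a survey before randomisation; and section 14.0 provides for ineligibility found during baseline. The coercion exclusion can hardly be applied without asking the partner, which suggests that some direct questioning is intended. Section 13.0 describes the REDCap screener as completed by the potential participant, which does not rule out the partner. The survey content, the screener and the network procedures are not in the documents, so sites may already be asking.

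Much of this stands. A reader might infer that nobody but the index is ever screened, so that an ineligible partner enters purely on the index's word. The documents do not support that: they leave the partner check unspecified. Reach to both partners is explicit only for violence and coercion; for psychiatric symptoms and ideation it is inferred from the couple heading.

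What does not stand is the suggestion that these safeguards close the gap. None is described as putting the exclusions to the partner, none is described as a gate before allocation, and consent and baseline steps for a later-joining partner are not tied to any eligibility check.

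**Conclusion.** The concern holds as a gap in a stated method. The protocol describes screening by proxy for criteria that reach both partners, and does not say how, when or by whom those criteria are confirmed with the partner before randomisation and a same-day joint session, or when a partner joins later. It deserves correction because it bears on safety and is cheap to close.

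Its size cannot be estimated. A reader might multiply an assumed prevalence of partner violence by an assumed rate of non-disclosure to obtain a count of wrongly admitted couples. The documents give neither rate, such a count would ignore detection during consent or baseline, and it would include IHTC couples, who have no joint session. A reader might also infer that late-found ineligibility would surface more often in the We Test arm because contact is longer. No section supports this, and IHTC couples are seen individually, which could equally favour disclosure.

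The conclusion rests on the two documents alone. If the survey or the network procedures already put the exclusions to each partner before allocation, the remaining defect is that the protocol does not say so.

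**What to change.** In section 6.0 (including the Phase 3 baseline list) and section 13.0, require each participating partner to complete the existing REDCap screener himself and in private: before randomisation when a couple attends together, and before enrolment when a partner joins later. State who reviews the result, and that it is handled so that one partner's answers are not revealed to the other. If sites already do this, a sentence in each place is enough.

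Reconcile sections 6.0, 10.0 and 14.0 on what happens to an already randomised index whose partner is then found ineligible. A blanket rule that the index always continues in his arm and in follow-up would not fit the present text: the violence exclusion in 10.0 applies to the couple, so the index may meet it too, and 14.0 takes people found ineligible after baseline off the follow-up call lists. The protocol should settle this explicitly, including the case where the reason is violence.

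The cost is protocol wording and a few minutes per partner, since section 13.0 already provides the screener by iPad, phone or online link. Some couples will be screened out. The less obvious cost is inadvertent disclosure: turning a couple away straight after a private screen may signal what one partner said, so the handling of results needs care.
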